4.6.3 Study Discontinuation

The Sponsor has the right to terminate this study at any time. Reasons for terminating the study may include, but are not limited to, the following:

- The incidence or severity of adverse events in this or other studies indicates a potential health hazard to patients
- Patient enrollment is unsatisfactory

The Sponsor will notify the investigator if the Sponsor decides to discontinue the study.

4.6.4 Site Discontinuation

The Sponsor has the right to close a site at any time. Reasons for closing a site may include, but are not limited to, the following:

- Excessively slow recruitment
- Poor protocol adherence
- Inaccurate or incomplete data recording
- Non-compliance with the International Council for Harmonisation (ICH) guideline for Good Clinical Practice
- No study activity (i.e., all patients have completed the study and all obligations have been fulfilled)

5. ASSESSMENT OF SAFETY

5.1 SAFETY PLAN

MSTT1041A is not approved, and clinical development is ongoing. The safety plan for patients in this study is based on clinical experience with MSTT1041A in completed Phase I studies and an ongoing Phase IIb study. As reported in the MSTT1041A Investigator's Brochure, there are no identified risks associated with MSTT1041A and there were no serious adverse events or adverse events that led to treatment discontinuation in healthy subjects who received single (n=79) or multiple (n=31) SC doses of MSTT1041A ranging from 2.1 to 560 mg and IV doses ranging from

210 to 700 mg, or in patients with atopic asthma (n=2) who received a single 700 mg IV dose of MSTT1041A.

To date, a Phase IIb study with MSTT1041A in patients with severe asthma is currently ongoing. In this study, 502 patients were randomized to a 52-week double-blind treatment period and received blinded study treatment (70 mg, 210 mg, 490 mg of MSTT1041A, or placebo). Refer to the MSTT1041A Investigator's Brochure for a complete summary of safety information.

Several measures will be taken to ensure the safety of patients participating in this study. Eligibility criteria have been designed to exclude patients at higher risk for toxicities. Patients will undergo safety monitoring during the study, including assessment of the nature, frequency, and severity of adverse events. In addition, guidelines for managing adverse events, including criteria for treatment interruption or discontinuation, are provided below.

5.1.1 Risks Associated with MSTT1041A

5.1.1.1 Immunogenicity

As with administration of any exogenous protein, there is potential risk for development of ADAs. Such antibodies can be neutralizing with potential for reduced therapeutic effect of the drug and/or sensitizing with potential for adverse events.

Serum samples will be collected at protocol-defined intervals to monitor for the development of ADAs. Patients who have clinical sequelae that are considered potentially related to an ADA response may also be asked to return for additional follow-up testing.

Refer to the MSTT1041A Investigator's Brochure for details on immunogenicity.

5.1.1.2 Hypersensitivity Reactions and Anaphylaxis/Hypersensitivity-Like Reactions

Hypersensitivity reactions and anaphylaxis have been described with SC administration of monoclonal antibodies (Corominas et al. 2014). Signs and symptoms may include acute onset (minutes to several hours) of one or more of the following: respiratory compromise, reduced blood pressure, skin-mucosal involvement, or gastrointestinal symptoms (Sampson et al. 2006).

The potential for hypersensitivity to MSTT1041A in humans is unknown. However, as with any large-molecule therapeutic, administration of MSTT1041A may result in systemic reactions. Systemic reactions to large-molecule therapeutics can be IgE or non-IgE mediated or due to the release of cytokines and are generally characterized by signs and symptoms such as skin rash, urticaria, pruritus, local or diffuse erythema, angioedema, fever, chills, cough, dyspnea, wheezing, bronchospasm, nausea, vomiting, diaphoresis, chest pain, tachycardia or bradycardia, and/or hypotension, which can be

severe or life threatening. Effects typically occur during or within several hours after drug administration, but they may be delayed. Patients with a history of anaphylaxis, hypersensitivities to a biologic agent, or known hypersensitivity to any component of the MSTT1041A or placebo injection will be excluded from the study (see Section 4.1.2).

Investigators and health care professionals administering MSTT1041A should monitor patients after drug administration as described in Section 4.3.2.1. Investigators and staff should recognize and manage the signs and symptoms of such reactions and should be familiar with Sampson's criteria for defining anaphylaxis (Sampson et al. 2006). All potential cases of anaphylaxis should be captured on the appropriate eCRF as instructed in Section 5.2 and Section 5.3. Investigators and health care professionals should accurately report these events immediately to the Sponsor as serious adverse events if appropriate. Health care professionals should also instruct patients on how to recognize the symptoms of any such events and to contact a health care provider or seek emergency care in case of any such symptoms.

Refer to the MSTT1041A Investigator's Brochure for details on hypersensitivity reactions and anaphylaxis/hypersensitivity-like reactions.

5.1.1.3 Injection-Site Reactions

Injection-site reactions have been described with SC administration of monoclonal antibodies (Corominas et al. 2014). Signs and symptoms may include pain, itching, erythema, and swelling at the injection site. The reaction may be immediate, although it usually appears within 24–48 hours with variable incidence according to the drug administered.

No clinically significant injection-site reactions associated with MSTT1041A were observed following single or repeat doses in cynomolgus monkeys or healthy volunteers. However, as with any large-molecule therapeutic, administration of MSTT1041A may result in local reactions. Local reactions may include signs and symptoms such as redness, tenderness or pain, bruising, warmth, swelling, pruritus, or infection.

During the study, all injection-site events should be accurately reported on the appropriate eCRF.

Refer to the MSTT1041A Investigator's Brochure for details on injection-site reactions.

5.1.1.4 Infection

The intended mechanism of action of MSTT1041A suggests inhibitory effects on immune responses mediated by Th2 cells, leading to the possibility of a decrease in the protective response to infection, particularly helminthic infections (Molofsky et al. 2015). All study participants will be monitored for signs and symptoms suggestive of infection by collection of vital signs, clinical laboratory tests, and adverse events.

Refer to the MSTT1041A Investigator's Brochure for details on infections.

5.1.1.5 Exacerbation of Cardiovascular Disease

Published studies involving mouse models of cardiovascular disease or in vitro culture systems describe potential cardioprotective and atheroprotective roles of the IL-33/ST2 axis (Sanada et al. 2007; Miller et al. 2008; Seki et al. 2009; McLaren et al. 2010; Wasserman et al. 2012). For example, after experimentally induced acute left ventricular pressure overload, which could be relevant to clinical scenarios involving increased afterload (e.g., left-sided congestive heart failure or acute hypertension), ST2 mice had more left ventricular hypertrophy, more fibrosis, and impaired survival relative to their wild-type littermates (Sanada et al. 2007). However, the translatability of these findings remains uncertain. In addition, studies with conflicting data exist (Abston et al. 2012; Demyanets et al. 2013; Martin et al. 2015). In nonclinical toxicology and safety pharmacology studies with cynomolgus monkeys, including a 28-day and 6-month, repeat-dose toxicology study as well as a single-dose, cardiovascular safety study in telemetrized animals, no biologically significant changes were exhibited by MSTT1041A.

Evidence has shown that the ST2 receptor is a prognostic biomarker of cardiovascular disease outcome (Sabatine et al. 2008; Shah et al. 2009; Weir et al. 2010). Although published findings suggest a possible risk of exacerbation of existing cardiovascular disease in humans, there are no identified cardiovascular risks associated with inhibiting the IL-33/ST2 axis in humans.

Patients with active or unstable recent cardiovascular disease will be excluded from the study. Cardiac safety will be evaluated with monitoring of vital signs, ECG assessments, the collection of relevant adverse events, and other assessments described in the protocol. To monitor other factors that may affect cardiovascular risk, HbA_{1c}, fasting glucose, and lipid panels will be monitored to observe for indication of possible atherogenic and metabolic effects of MSTT1041A exposure.

During the study, all major adverse cardiac events (MACE) should be accurately reported on the appropriate eCRF. MACE include death due to cardiovascular causes, non-fatal myocardial infarction, non-fatal stroke or transient ischemic attack, unstable angina, or chest pain requiring hospitalization, coronary revascularization, and congestive heart failure requiring hospitalization.

Refer to the MSTT1041A Investigator's Brochure for details on cardiovascular disease.

5.1.2 Management of Patients Who Experience Adverse Events

5.1.2.1 Treatment Interruption

MSTT1041A treatment may be temporarily suspended in patients who experience toxicity considered to be related to study drug. If MSTT1041A has been withheld for two or more consecutive dosing visits because of toxicity, the patient should be discontinued from MSTT1041A, unless resumption of treatment is approved following investigator discussion with the Medical Monitor. MSTT1041A treatment may be suspended for reasons other than toxicity (e.g., surgical procedures) with Medical Monitor approval.

The investigator and the Medical Monitor will determine the acceptable length of treatment interruption.

Note: For treatment interruption because of rescue treatment, see Section 4.3.4.

5.1.2.2 Management Guidelines

Table 1 provides specific guidelines for withholding or discontinuing study drug for patients who experience hepatotoxicity.

Table 1 Guidelines for Treatment Interruption or Discontinuation for Patients Who Experience Hepatotoxicity

Event	Action to Be Taken
Hepatotoxicity	
ALT or AST increase that meets Hy's Law criteria: ALT or AST $>3 \times$ ULN in combination with TBIL $>2 \times$ ULN or clinical jaundice ruling out other medical sequels to explain the combination of increased aminotransferase and serum total bilirubin.	Discontinue MSTT1041A.
If abnormal liver tests, but the criteria for Hy's Law are not met: ALT or AST increase that meets at least one of the following criteria: 
• $>8 \times$ ULN• $>5 \times$ ULN for ≥ 2 weeks• $>3 \times$ ULN with clinical signs or symptoms that are consistent with hepatitis (e.g., right upper quadrant pain or tenderness, fever, nausea, vomiting, jaundice)	Withhold MSTT1041A. Treatment may be resumed if an alternative cause is identified and laboratory values have resolved to those at the randomization visit. If signs or symptoms recur, permanently discontinue MSTT1041A.
If abnormal liver tests, but the criteria for Hy's Law are not met: TBIL $>3 \times$ ULN	Consider withholding MSTT1041A. Treatment may be resumed if an alternative cause is identified and laboratory values have resolved to those at the randomization visit. If signs or symptoms recur, permanently discontinue MSTT1041A.
ALP $>3 \times$ ULN	Consider withholding MSTT1041A. Treatment may be resumed if an alternative cause is identified and laboratory values have resolved to those at the randomization (Day 1) visit. If signs or symptoms recur, permanently discontinue MSTT1041A.

TBIL = total bilirubin; ULN = upper limit of normal.

5.1.2.3 Management of Increases in QT Interval

Study drug should be discontinued in patients who develop any of the following, unless there is a clear alternative cause for the changes:

- Sustained (at least two ECG measurements >30 minutes apart) QTcF that is >500 ms and >60 ms longer than the baseline value
- Sustained absolute QTcF that is >515 ms
- An episode of torsades de pointes or a new ECG finding of clinical concern

Of note, if there is a new intraventricular conduction block, the increase in QRS complex duration should be subtracted from the QTcF change, because this represents an increase in QTcF unrelated to alterations in repolarization. Also of note, it is not uncommon to record arrhythmias such as non-sustained ventricular tachycardia, supraventricular tachycardia, pauses, or atrial fibrillation in healthy volunteers receiving placebo during periods of extended ECG monitoring. Therefore, it is critical that expert cardiology advice be sought to confirm any ECG changes and to ascertain the likelihood of a drug-induced arrhythmia versus the background occurrence of this arrhythmia. In such a situation, saving all available ECG data is highly suggested.

Management of patients with sustained QTcF prolongation should include close monitoring, with ECGs repeated at least hourly until two successive ECGs show resolution of the findings, correction of any electrolyte abnormalities, and possible discontinuation of other concomitant medications that are known to prolong the QT interval. Consultation with a cardiologist or electrophysiologist is recommended to help in the management of such patients.

In rare circumstances, it may be acceptable to resume study drug at a lower dose, provided that any ECG abnormalities have resolved and the patient is appropriately monitored. Clinical judgment should be applied.

5.1.2.4 Anaphylaxis

Anaphylaxis should be promptly assessed and treated per local standard of care. For current guidelines, refer to Campbell et al. 2014:

<https://www.aaaai.org/Aaaai/media/MediaLibrary/PDF%20Documents/Practice%20and%20Parameters/Anaphylaxis-Practice-Parameter-2014.pdf>

In accordance with the current guidelines, the measurement of tryptase (serum or plasma) and histamine (plasma) levels should be considered to support a diagnosis of anaphylaxis, although clinicians should treat anaphylaxis regardless of the availability of the results of these tests.

During the study, all anaphylaxis events should be accurately reported on the appropriate eCRF.

5.2 SAFETY PARAMETERS AND DEFINITIONS

Safety assessments will consist of monitoring and recording adverse events, including serious adverse events and adverse events of special interest, performing protocol-specified safety laboratory assessments, measuring protocol-specified vital signs, and conducting other protocol-specified tests that are deemed critical to the safety evaluation of the study.

Certain types of events require immediate reporting to the Sponsor, as outlined in Section [5.4](#).

5.2.1 Adverse Events

According to the ICH guideline for Good Clinical Practice, an adverse event is any untoward medical occurrence in a clinical investigation subject administered a pharmaceutical product, regardless of causal attribution. An adverse event can therefore be any of the following:

- Any unfavorable and unintended sign (including an abnormal laboratory finding), symptom, or disease temporally associated with the use of a medicinal product, whether or not considered related to the medicinal product
- Any new disease or exacerbation of an existing disease (a worsening in the character, frequency, or severity of a known condition) (see Sections [5.3.5.10](#) and [5.3.5.11](#) for more information)
- Recurrence of an intermittent medical condition (e.g., headache) not present at baseline
- Any deterioration in a laboratory value or other clinical test (e.g., ECG, X-ray) that is associated with symptoms or leads to a change in study treatment or concomitant treatment or discontinuation from study drug
- Adverse events that are related to a protocol-mandated intervention, including those that occur prior to assignment of study treatment (e.g., screening invasive procedures such as biopsies)

5.2.2 Serious Adverse Events (Immediately Reportable to the Sponsor)

A serious adverse event is any adverse event that meets any of the following criteria:

- Is fatal (i.e., the adverse event actually causes or leads to death)
- Is life threatening (i.e., the adverse event, in the view of the investigator, places the patient at immediate risk of death)

This does not include any adverse event that, had it occurred in a more severe form or was allowed to continue, might have caused death.

- Requires or prolongs inpatient hospitalization (see Section [5.3.5.12](#))

- Results in persistent or significant disability/incapacity (i.e., the adverse event results in substantial disruption of the patient's ability to conduct normal life functions)
- Is a congenital anomaly/birth defect in a neonate/infant born to a mother exposed to study drug
- Is a significant medical event in the investigator's judgment (e.g., may jeopardize the patient or may require medical/surgical intervention to prevent one of the outcomes listed above)

The terms "severe" and "serious" are not synonymous. Severity refers to the intensity of an adverse event (e.g., rated as mild, moderate, severe, or life-threatening according to WHO Adverse Drug Reaction Terminology; see Section 5.3.3); the event itself may be of relatively minor medical significance (such as severe headache without any further findings).

Severity and seriousness need to be independently assessed for each adverse event recorded on the eCRF.

Serious adverse events are required to be reported by the investigator to the Sponsor immediately (i.e., no more than 24 hours after learning of the event; see Section 5.4.2 for reporting instructions).

5.2.3 Adverse Events of Special Interest (Immediately Reportable to the Sponsor)

Adverse events of special interest are required to be reported by the investigator to the Sponsor immediately (i.e., no more than 24 hours after learning of the event; see Section 5.4.2 for reporting instructions). Adverse events of special interest for this study are as follows:

- Cases of potential drug-induced liver injury that include an elevated ALT or AST in combination with either an elevated bilirubin or clinical jaundice, as defined by Hy's Law (see Section 5.3.5.8)
- Suspected transmission of an infectious agent by the study drug, as defined below

Any organism, virus, or infectious particle (e.g., prion protein transmitting transmissible spongiform encephalopathy), pathogenic or non-pathogenic, is considered an infectious agent. A transmission of an infectious agent may be suspected from clinical symptoms or laboratory findings that indicate an infection in a patient exposed to a medicinal product. This term applies only when a contamination of the study drug is suspected.
- Anaphylaxis, anaphylactoid, and hypersensitivity reactions
- MACE, including death due to cardiovascular causes, non-fatal myocardial infarction, non-fatal stroke or transient ischemic attack, unstable angina, or chest pain requiring hospitalization, coronary revascularization, and congestive heart failure requiring hospitalization

5.3 METHODS AND TIMING FOR CAPTURING AND ASSESSING SAFETY PARAMETERS

The investigator is responsible for ensuring that all adverse events (see Section [5.2.1](#) for definition) are recorded on the Adverse Event eCRF and reported to the Sponsor in accordance with instructions provided in this section and in Sections [5.4–5.6](#).

For each adverse event recorded on the Adverse Event eCRF, the investigator will make an assessment of seriousness (see Section [5.2.2](#) for seriousness criteria), severity (see Section [5.3.3](#)), and causality (see Section [5.3.4](#)).

5.3.1 Adverse Event Reporting Period

Investigators will seek information on adverse events at each patient contact. All adverse events, whether reported by the patient or noted by study personnel, will be recorded in the patient's medical record and on the Adverse Event eCRF.

After informed consent has been obtained but prior to initiation of study drug, only serious adverse events caused by a protocol-mandated intervention (e.g., invasive procedures such as biopsies, discontinuation of medications) should be reported (see Section [5.4.2](#) for instructions for reporting serious adverse events).

After initiation of study drug, all adverse events will be reported until 12 weeks after the final dose of study drug.

Instructions for reporting adverse events that occur after the adverse event reporting period are provided in Section [5.6](#).

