4.6 TREATMENT, PATIENT, STUDY, AND SITE DISCONTINUATION

4.6.1 Study Treatment Discontinuation

Patients must permanently discontinue study treatment if they experience any of the following:

- Any medical condition that the investigator or Sponsor determines may jeopardize the patient's safety if he or she continues to receive study treatment
- Investigator or Sponsor determination that treatment discontinuation is in the best interest of the patient
- Pregnancy
- Cases of potential drug-induced liver injury that include an elevated ALT or AST in combination with either an elevated bilirubin or clinical jaundice, as defined by Hy's Law (see Section 5.3.5.8)

The primary reason for study treatment discontinuation should be documented on the appropriate eCRF. Every effort should be made to retain patients in the study. All patients will be asked to complete all study visits and assessments regardless of discontinuation of study treatment. Patients who discontinue study treatment prematurely will not be replaced.

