5.3.5.9 Deaths

All deaths that occur during the protocol-specified adverse event reporting period (see Section [5.3.1](#)), regardless of relationship to study drug, must be recorded on the Adverse Event eCRF and immediately reported to the Sponsor (see Section [5.4.2](#)).

Death should be considered an outcome and not a distinct event. The event or condition that caused or contributed to the fatal outcome should be recorded as the single medical concept on the Adverse Event eCRF. Generally, only one such event should be reported. If the cause of death is unknown and cannot be ascertained at the time of reporting, "**unexplained death**" should be recorded on the Adverse Event eCRF. If the cause of death later becomes available (e.g., after autopsy), "unexplained death" should be replaced by the established cause of death. The term "**sudden death**" should not be used unless combined with the presumed cause of death (e.g., "sudden cardiac death").

Deaths that occur after the adverse event reporting period should be reported as described in Section 5.6.

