5.4.2.2 Events That Occur after Study Drug Initiation

After initiation of study drug, serious adverse events and adverse events of special interest will be reported until 12 weeks after the final dose of study drug. Investigators should record all case details that can be gathered immediately (i.e., within 24 hours after learning of the event) on the Adverse Event eCRF and submit the report via the electronic data capture (EDC) system. A report will be generated and sent to Safety Risk Management by the EDC system.

In the event that the EDC system is unavailable, the paper Clinical Trial Serious Adverse Event/Adverse Event of Special Interest Reporting Form provided to investigators should be completed and submitted to the Sponsor or its designee immediately (i.e., no more than 24 hours after learning of the event), either by faxing or by scanning and emailing the form using the fax number or email address provided to investigators. Once the EDC system is available, all information will need to be entered and submitted via the EDC system.

Instructions for reporting serious adverse events that occur > 12 weeks after the final dose of study treatment are provided in Section 5.6.

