5.4.3 Reporting Requirements for Pregnancies

5.4.3.1 Pregnancies in Female Patients

Female patients of childbearing potential will be instructed to immediately inform the investigator if they become pregnant during the study or within 12 weeks after the final dose of study drug. A paper Clinical Trial Pregnancy Reporting Form should be completed and submitted to the Sponsor or its designee immediately (i.e., no more than 24 hours after learning of the pregnancy), either by faxing or by scanning and emailing the form using the fax number or email address provided to investigators. Pregnancy

should not be recorded on the Adverse Event eCRF. The investigator should discontinue study drug and counsel the patient, discussing the risks of the pregnancy and the possible effects on the fetus. Monitoring of the patient should continue until conclusion of the pregnancy. Any serious adverse events associated with the pregnancy (e.g., an event in the fetus, an event in the mother during or after the pregnancy, or a congenital anomaly/birth defect in the child) should be reported on the Adverse Event eCRF. In addition, the investigator will submit a Clinical Trial Pregnancy Reporting Form when updated information on the course and outcome of the pregnancy becomes available.

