5.6 ADVERSE EVENTS THAT OCCUR AFTER THE ADVERSE EVENT REPORTING PERIOD

The Sponsor should be notified if the investigator becomes aware of any serious adverse event that occurs after the end of the adverse event reporting period (defined as 12 weeks after the final dose of study drug), if the event is believed to be related to prior study drug treatment. These events should be reported through use of the Adverse Event eCRF. However, if the EDC system is not available, the investigator should report these events directly to the Sponsor or its designee, either by faxing or by scanning and emailing the paper Clinical Trial Serious Adverse Event/Adverse Event of Special Interest Reporting Form using the fax number or email address provided to investigators.

5.7 EXPEDITED REPORTING TO HEALTH AUTHORITIES, INVESTIGATORS, INSTITUTIONAL REVIEW BOARDS, AND ETHICS COMMITTEES

The Sponsor will promptly evaluate all serious adverse events and adverse events of special interest against cumulative product experience to identify and expeditiously communicate possible new safety findings to investigators, IRBs, ECs, and applicable health authorities based on applicable legislation.

To determine reporting requirements for single adverse event cases, the Sponsor will assess the expectedness of these events using the following reference document:

- MSTT1041A Investigator's Brochure

The Sponsor will compare the severity of each event and the cumulative event frequency reported for the study with the severity and frequency reported in the applicable reference document.

Reporting requirements will also be based on the investigator's assessment of causality and seriousness, with allowance for upgrading by the Sponsor as needed.

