Appendix 1: Schedule of Activities

- As clinically indicated.
- Urinalysis includes dipstick (pH, specific gravity, glucose, protein, ketones, blood) and microscopic examination (sediment, RBCs, WBCs, casts, crystals, epithelial cells, bacteria).
- If patient has not fasted for 8 hours, the patient must return to the site for fasting blood draw only. All other visit assessments should be completed within the regular visit.
- PK and ADA samples to be collected prior to study drug administration.
[REDACTED]
- Patients will receive 490 mg MSTT1041A or placebo at Day 1, Week 4, 8, and 12 visits administered as four SC injections (one in each quadrant of the abdomen). The dose at the Week 1 visit will be 245 mg MSTT1041A or placebo (loading dose) administered as two SC injections (see Section 4.3.2.1 for details).
- Medication (e.g., prescription drugs, over-the-counter drugs, vaccines, herbal or homeopathic remedies, nutritional supplements, emollients) used by a patient in addition to protocol-mandated treatment from 6 months before screening until 12 weeks after the final dose of study drug.
- After informed consent has been obtained but prior to initiation of study drug, only serious adverse events caused by a protocol-mandated intervention should be reported. After initiation of study drug, all adverse events will be reported until 12 weeks after the after the final dose of study drug. After this period, the Sponsor should be notified if the investigator becomes aware of any serious adverse event that is believed to be related to prior study drug treatment (see Section 5.6).

[figure not shown]
Appendix 2

WHO Classification of Topical Corticosteroids

The following table provides a non-exhaustive list of examples of topical corticosteroids classified by potency (Source: <http://apps.who.int/medicinedocs/en/d/Jh2918e/32.html>).

Potency	Class	Topical Corticosteroid	Formulation
Ultra High	I	Clobetasol propionate	Cream, 0.05%
		Diflorasone diacetate	Ointment, 0.05%
High	II	Amcinonide	Ointment, 0.1%
		Betamethasone dipropionate	Ointment, 0.05%
		Desoximetasone	Cream or ointment, 0.025%
		Fluocinonide	Cream, ointment or gel, 0.05%
		Halcinonide	Cream, 0.1%
		Betamethasone dipropionate	Cream, 0.05%
		Betamethasone valerate	Ointment, 0.1%
		Diflorasone diacetate	Cream, 0.05%
		Triamcinolone acetonide	Ointment, 0.1%
		Desoximetasone	Cream, 0.05%
		Fluocinolone acetonide	Ointment, 0.025%
		Fludroxcortide	Ointment, 0.05%
		Hydrocortisone valerate	Ointment, 0.2%

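### Safety reporting ends 12 weeks after the last dose, so patients who stop treatment early but stay in the study have scheduled follow-up in which some events fall outside the reporting rule, in conflict with other text

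*Combined protocol and SAP*

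**What the plan says.** **The limit.** Section 5.3.1: "After initiation of study drug, all adverse events will be reported until 12 weeks after the final dose of study drug". Section 5.4.2.2 says that "serious adverse events and adverse events of special interest will be reported until 12 weeks after the final dose of study drug". The Appendix 1 footnote on adverse events repeats the rule. The footnote on concomitant medications collects them "from 6 months before screening until 12 weeks after the final dose of study drug".

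**Deaths.** Section 5.3.5.9 requires recording, whatever the cause, for "All deaths that occur during the protocol-specified adverse event reporting period". It then adds: "Deaths that occur after the adverse event reporting period should be reported as described in Section 5.6".

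**After the limit.** Section 5.6 asks for notification of a serious event "if the event is believed to be related to prior study drug treatment".

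**Who is still attending.** Section 4.6.1: "All patients will be asked to complete all study visits and assessments regardless of discontinuation of study treatment". Section 4.3.4 says the same of patients who receive rescue or do not complete treatment, and 4.3.2.1 asks patients who cannot tolerate study drug to continue assessments.

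**Text that points the other way.** The first paragraph of 5.3.1 has investigators ask about adverse events at every contact and record all of them in the chart and on the eCRF. Section 5.3.2 covers all evaluation timepoints. Appendix 1 marks adverse events and concomitant medications at every visit. Section 4.4 gives a start but no end for medication recording. The treatment-emergent definition in 6.5 has no end date.

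**The concern.** The window is counted from the last dose, while the visit schedule runs to Week 24 whether or not the patient is still on treatment. A patient who stops early and stays, as the protocol asks, therefore outlives the reporting window while still being seen. Two instructions then apply to the same visit, and sites may follow either.

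Two things are at stake. First, Section 6.5 summarises adverse event incidence by arm. Stopping treatment may be related to outcome; for instance, Section 4.3.4 requires study treatment to be discontinued after systemic rescue. If stopping differs by arm, the time over which events are captured can differ too. Events of special interest (5.2.3) include cardiovascular events and hypersensitivity reactions, for which complete capture matters most.

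Second, Section 4.3.4 counts rescue during the treatment period as treatment failure, and rescue is known partly through medication records. A medication cut-off before Week 16 would touch that classification.

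**Working it through.** **Inputs.** Dosing days from Appendix 1: Day 1, Day 8 (Week 1), Day 29 (Week 4), Day 57 (Week 8), Day 85 (Week 12). Window: 12 weeks = 84 days. Week 16 = Day 113; Week 24 = Day 169.

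**Formula.** Window end = day of last dose + 84. Uncovered time = 169 − window end.

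**The plan's own case.** Last dose at Week 12: 85 + 84 = 169. On nominal days the window meets the end of study exactly.

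| Last dose | Window end | Days uncovered to Day 169 | Days uncovered before Day 113 | Scheduled visits outside |
|---|---|---|---|---|
| Day 1 | 1 + 84 = 85 | 84 | 28 | Weeks 14, 16, 20, 24 |
| Day 8 | 8 + 84 = 92 | 77 | 21 | Weeks 14, 16, 20, 24 |
| Day 29 | 29 + 84 = 113 | 56 | 0 | Weeks 20, 24 |
| Day 57 | 57 + 84 = 141 | 28 | 0 | Week 24 |
| Day 85 | 85 + 84 = 169 | 0 | 0 | none |

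**Visit windows.** A Week 12 dose given 4 days early (Day 81) closes the window at Day 165, which is 9 days before a Week 24 visit held 5 days late (Day 174). A Week 4 dose given 4 days early (Day 25) closes it at Day 109, just before Week 16.

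**What falls outside after the window.** Under 5.3.5.9 and 5.6 together: non-serious events, including non-serious events of special interest, and serious events or deaths judged unrelated. Serious events believed related, fatal ones included, remain notifiable.

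**Size, by assumption only.** The documents do not say how many patients will stop and stay; the 25% in Section 6.1 is dropout, a different quantity. Suppose the event hazard is constant and equal in both arms, 60% have at least one event over 168 days, and 25% of placebo and 10% of active patients stop after the Week 4 dose but stay.

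- Incidence recorded over 112 days: 1 − 0.4^(112/168) = 45.7%.
- Placebo: 0.75 × 60 + 0.25 × 45.7 = 56.4%.
- Active: 0.90 × 60 + 0.10 × 45.7 = 58.6%.
- Spurious difference: about 2.1 points, or 0.021 × 45 ≈ 1 patient in an arm of 45.
- Standard error of a difference at 60% in both arms: √(2 × 0.6 × 0.4 / 45) = 10.3 points.
- Event follow-up lost: 0.25 × 56/168 = 8.3% on placebo, 0.10 × 56/168 = 3.3% on active.

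If the same patients stopped after the Week 8 dose, 28 days rather than 56 would be lost, and the follow-up losses would halve to 4.2% and 1.7%.

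**The case against.** The best defence is that collection is already instructed at the visits in question. The opening of 5.3.1, 5.3.2 and the Appendix 1 boxes all call for it, and 5.4 asks for serious events whatever their relationship to drug. After the window 5.6 still captures serious events believed related, and 5.3.4 makes related the default unless there is evidence of another cause or the timing is implausible, so an unexplained death or cardiac event is not automatically lost. A window of 12 weeks from last exposure is coherent: it equals the contraception period in 4.1.1 and lands on Week 24 for a fully dosed patient. The pregnancy rule, which applies "if they become pregnant during the study or within 12 weeks after the final dose of study drug", serves another purpose, so its different end is not a contradiction.

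Most of this stands, and it rules out the strongest reading. A reader might infer that safety events after the window cannot be reported at all; 5.6 and the every-contact instruction do not support that. What the defence does not remove is the conflict itself. One section tells sites both to record everything at each contact and to stop at 12 weeks, and an exposure-based window gives no reason to stop while the patient is still being examined.

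On rescue, a reader might infer that treatment failures before Week 16 will go unrecorded. The documents do not support that either. The cut-off appears only in a footnote. Section 4.4 sets no end, Section 3.1 has telephone visits ask about concomitant medications, and 4.5.2 asks for medication changes at follow-up examinations. On nominal days the gap concerns only patients whose last dose was Day 1 or Week 1, who stay, and whose first rescue falls in the last 28 or 21 days before Week 16. Patients who stopped because of systemic rescue are already failures, and topical rescue does not stop treatment.

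**Conclusion.** The concern holds as a minor point. The date arithmetic is certain: anyone who stays after a last dose before Week 12 has 28 to 84 days of planned follow-up beyond the reporting limit. In that time the text is contradictory for non-serious events and for serious events or deaths judged unrelated. The likely harm is uneven collection between sites and, if stopping differs by arm, unequal follow-up for events.

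It would be too strong to say that the arm with more stopping will look materially safer. The scenario above rests wholly on assumed rates, and its 2-point shift is far inside the sampling error of a descriptive summary. The true size cannot be derived from the documents and is probably small.

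The medication footnote is a secondary inconsistency to be reconciled with Section 4.4 and the schedule. It is not a clear bar on recording rescue and gives no ground for doubting the primary endpoint.

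**What to change.** In Sections 5.3.1, 5.4.2.2 and 5.6 and in both Appendix 1 footnotes (adverse events and concomitant medications), end the window at the patient's last study visit or 12 weeks from the final dose of study drug, whichever is later. Section 5.3.5.9 then follows by cross-reference. The pregnancy rule in 5.4.3.1 already covers both periods and can serve as the drafting model.

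Uncovered time falls to zero for everyone who stays to the last visit, including where visit windows slip, and the text agrees with the Appendix 1 boxes. Patients who leave the study keep the present 12-week rule.

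The cost is wording in an amendment and in the eCRF completion guideline. No visit or procedure is added, since these patients are already asked to attend. The one downside is that some additional events unrelated to drug will be recorded in early stoppers.
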